5.0 DOSING DELAYS/DOSE MODIFICATIONS

5.1 Dose Modifications for sEphB4-HSA

If any participant develops major bleeding or any unexpected grade 4 or greater event on study, accrual will be held until the PI and sponsor assess the need for changes to prophylaxis or changes to protocol or consent. In the event accrual is stopped, accrual will not resume until CTEP has reviewed the decision in the case where the PI and Sponsor feel no consent or protocol changes were needed. Dose modifications for other toxicities will be allowed and are described below. Participants requiring a delay of > 28 days (4 weeks) due to drug-related toxicity will be removed from the study.

When there is a dose modification, the participant should be notified of the change in dose.

Table 5-A: Dose modifications

LEVEL	DOSE	SCHEDULE
0	10 mg/kg	Days 1 and 15 (28 day cycle)
-1	7.5mg mg/kg	Days 1 and 15 (28 day cycle)
-2	5.0 mg/kg	Days 1 and 15 (28 day cycle)

5.2 Dose Modifications for Non-Hematologic Toxicity (EXCEPT hypertension)

See [Section 5.4](#) for dose modifications for hypertension.

Symptomatic grade 2 toxicity

If the participant experiences a new symptomatic grade 2 non-hematologic toxicity, sEphB4-HSA will be withheld until the toxicity has resolved to \leq grade 1. sEphB4-HSA will then be resumed at the same weekly dose. If the symptomatic grade 2 toxicity recurs despite optimal supportive care (e.g., fluids, electrolyte replacement, anti-diarrheal medications), sEphB4-HSA will be withheld until the toxicity has resolved to \leq grade 1, and the weekly dose may be reduced by one dose level. If symptomatic grade 2 toxicity recurs at the reduced dose, sEphB4-HSA treatment will be discontinued.

Grade 3 or 4 toxicity

If the participant experiences grade 3/4 non-hematologic toxicity, sEphB4-HSA must be withheld until the toxicity has resolved to \leq grade 1 or baseline. sEphB4-HSA will then be resumed at a weekly dose that is reduced by one dose level. If the grade 3/4 toxicity recurs at the lower dose (level -1) dosing, sEphB4-HSA treatment will be stopped. If any participant experiences Steven-Johnson Syndrome, major allergic reaction which requires epinephrine, grade 3 neuropathy lasting at least 4 weeks, or grade 4 non-hematological toxicity that does not resolve with optimal supportive care (e.g., fluids, electrolyte replacement, anti-diarrheal medications), sEphB4-HSA must be discontinued, and the participant taken off study.

See below for a summary of dose modifications for non-hematologic toxicities.

Table 5-B: Summary of dose modifications for non-hematologic toxicity (except for hypertension)

OCCURRENCE	SYMPTOMATIC GRADE 2	GRADE 3/4
1 st	Hold until \leq grade 1, then resume at same dose	Hold until \leq grade 1 or baseline, then reduce sEphB4-HSA by one dose level
2 nd	Hold until \leq grade 1 then reduce dose by one dose level. If the dose is a lowest level, sEphB4-HSA may be stopped	Stop treatment
3 rd	Stop treatment	N/A

5.3 Dose Modifications for Renal Toxicity

If any participant experiences renal failure or renal toxicity with $\text{CrCl} < 60 \text{ mL/min}$ (calculated by modified Cockcroft-Gault method or 24-hour collection method at the Investigator's discretion), sEphB4-HSA must be withheld until toxicity has resolved. Serum creatinine must be evaluated weekly until returns to baseline. If renal toxicity does not resolve within 7 days, and CrCl is $> 30 \text{ mL/min}$ (calculated by Cockcroft-Gault method or 24-hour collection method at the Investigator's discretion), then sEphB4-HSA may be restarted at the next lowest dose level. If renal toxicity recurs and is felt to be related to sEphB4-HSA, and/or with $\text{CrCl} < 30 \text{ mL/min}$ (calculated by Cockcroft-Gault method or 24-hour collection method at the Investigator's discretion), then sEphB4-HSA treatment will be stopped.

If any participant experiences proteinuria, defined as $\geq 2+$ proteinuria on urinalysis, the following will be done.

If urine dipstick results are:

- 1) Negative, trace, or 1+ protein: proceed with administration of study drug.
- 2) 2+ protein: Proceed with study drug and collect 24-hour urine within 3 days before next cycle
 - 24-hour proteinuria $< 2 \text{ g}$: Give study drug. Continue to follow by 24-hour urinary protein before each cycle. If urinary protein falls to $< 1 \text{ g}$, resume monitoring by dipstick method.
 - 24-hour proteinuria $\geq 2 \text{ g}$: Hold study drug and repeat 24-hour urine collection for proteinuria before the next planned dose.
 - o Repeat 24-hour proteinuria $< 2 \text{ g}$: Give study drug and continue to check 24-hour protein before each cycle. If protein decreases to $< 1 \text{ g}$, resume monitoring by dipstick urinalysis.
 - o Repeat 24-hour urine $\geq 2 \text{ g}$: Hold study drug and continue to check before each dose of planned treatment. Give study drug if protein decreases to $< 2 \text{ g}$. If not $< 2 \text{ g}$ after 3 planned doses, discontinue study drug.

- 3) 3+ proteinuria: Hold and check 24-hour urinary protein. Restart study drug if 24-hour urinary protein decreases to <2 g. If not <2 g after 3 planned doses, discontinue study drug.
- 4) Grade 4: Discontinue study drug.

5.4 Dose Modifications for Hypertension

Hypertension: this is an expected AE within the class of anti-neoplastic drugs affecting the VEGF pathway. In participants with a baseline BP $\geq 120/80$ mm Hg and cardiac risk factors (history of hyperlipidemia, smoking, diabetes, treatment for hypertension, African-American ethnicity),⁶⁷ hypertension should be anticipated and therefore may need more aggressive management *prior to* first dose of study drug. In these cases, it is recommended that an internal medicine specialist or cardiologist be consulted to assist in management of hypertension. BPs are required at all visits prior to drug administration. All BP measurements should be made after the patient has been in a sitting or supine position for 5 minutes or longer.

Unless the patient has congestive heart failure, significant peripheral edema and/or significant salt intake that is difficult to modify, ACE inhibitors, ARBs and calcium channel blockers (nifedipine and amlodipine) may be more effective than diuretics.⁶⁸

Grade 2 Hypertension (systolic BP 140 - 159 mm Hg or diastolic BP 90 - 99 mm Hg)

Participants with grade 2 hypertension as documented by two or more different measurements - that are at least 30 minutes apart and measured by a healthcare provider - must be initiated on antihypertensive therapy per the treating physician. Treatment with sEphB4-HSA may continue during this time. BP should be rechecked 3-5 days after initiation of an antihypertensive, or after approximately 5 half-lives to allow antihypertensive drug levels to achieve steady state (~5 days for an antihypertensive dosed daily and ~3 days for one dosed twice daily). If systolic blood pressure (SBP) is still ≥ 140 mm Hg and/or diastolic blood pressure (DBP) is ≥ 90 mm Hg, physician should increase the dose of the antihypertensive or add additional antihypertensive therapy as indicated. Continue to monitor BP and titrate antihypertensives every 3-5 days until target BP (<140/90 mm Hg) is achieved.

Grade 3 Hypertension (systolic BP ≥ 160 mm Hg or diastolic BP ≥ 100 mm Hg)

In the case of grade 3 hypertension as documented by two or more different measurements - that are at least 30 minutes apart and measured by a healthcare provider - treatment with sEphB4-HSA must be held until hypertension returns to target BP (<140/90 mm Hg). Participants should be initiated on antihypertensive therapy, or if already on antihypertensive therapy, participants should have their antihypertensive therapy titrated, per the treating physician. BP should be rechecked 3-5 days after initiation or titration of antihypertensive therapy, or after approximately 5 half-lives to allow antihypertensive drug levels to achieve steady state (~5 days for an antihypertensive dosed daily and ~3 days for one dosed twice daily). If SBP is still ≥ 140 mm Hg and/or DBP is ≥ 90 mm Hg, the antihypertensive dose should be increased, or additional antihypertensive therapy added as indicated. Continue to monitor BP and titrate antihypertensives every 3-5 days until target BP (<140/90 mm Hg) is achieved. sEphB4-HSA should be held until hypertension returns to target BP (<140/90 mm Hg) and patient is asymptomatic, at which point sEphB4-HSA

[figure not shown]
treatment can be resumed.

If after subsequent dosing of sEphB4-HSA, grade 3 hypertension recurs - as documented by two or more different measurements that are at least one hour apart and measured by a healthcare provider - hold sEphB4-HSA and titrate antihypertensives as above until target BP (<140/90 mm Hg) is achieved. When subsequent dosing of sEphB4-HSA is restarted, patient will require reduction of sEphB4-HSA by one dose level.

If patient has to hold treatment for 4 weeks due to hypertension, sEphB4-HSA treatment will be discontinued.

All participants must be educated about the hypertension side effect and instructed to contact the study team if their BP remains under poor control between visits. It is recommended participants keep a BP log, but this is up to the treating physician's discretion.

Hypertension Management Schema

5.5 Dose Modifications for Hematologic Toxicity

Grade 1 or 2

There will be no dose interruptions or reductions for any grade 1/2 hematological toxicity.

Grade 3 or 4 Thrombocytopenia

If the participant experiences grade 3/4 thrombocytopenia, defined as a platelet count < 50 x 10⁹/L, sEphB4-HSA must be withheld until the toxicity has resolved to ≤ grade 2 within 14 days (2 weeks). sEphB4-HSA treatment may then be resumed at dose that is reduced by one dose level. If ≤ grade 2 not reached within 14 days (2 weeks), then stop treatment. If the grade 3/4 thrombocytopenia recurs after dose reduction, sEphB4-HSA must again be withheld until the toxicity level returns to < grade 2. If the toxicity again resolves to < grade 2 within two weeks, sEphB4-HSA may be recommenced, with the dose again reduced by one dose level. If sEphB4-HSA is at the lowest dose level, stop treatment. If, at any time,

the grade 3/4 toxicity persists for longer than two weeks, sEphB4-HSA will be stopped permanently. If grade 3 or 4 thrombocytopenia recurs at dose level 1, treatment will be stopped permanently. A grade 4 hematological toxicity lasting more than 4 weeks will be recorded as an unacceptable toxicity.

Table 5-C: Summary of dose modifications for thrombocytopenia

OCCURRENCE	GRADE 3/4
1 st	Hold until \leq grade 2 within 14 days (2 weeks), then resume at dose reduced by one dose level. If \leq grade 2 not reached within 14 days (2 weeks), then stop treatment.
2 nd	Hold until \leq grade 2 within 14 days (2 weeks), then resume at dose again reduced by one dose level. If at lowest dose level, stop treatment. If \leq grade 2 not reached in 14 days (2 weeks), then stop treatment.
3 rd (after 2 nd dose reduction)	Stop treatment.

Grade 3 or 4 Neutropenia

If a participant experiences grade 3/4 neutropenia, defined as an ANC $< 1 \times 10^9/L$, treatment with sEphB4-HSA may be interrupted and growth factor (filgrastim or pegfilgrastim) should be started at standard doses. If growth factor has already been started, growth factor should be continued (NOTE: Only the ANC, but not the white blood cell (WBC) count, will be considered in determining toxicity for purposes of dosage modification (i.e., doses should not be interrupted, or treatment modified for a WBC $< 2.0 \times 10^9/L$ if the ANC is $\geq 1 \times 10^9/L$)).

If the ANC returns to \leq grade 2 within 1 week without any additional toxicity (i.e., fevers), treatment with sEphB4-HSA may continue without dose modification with continued growth factor support.

If the ANC fails to return to \leq grade 2 within one week with growth factor support, or if additional toxicity seen (i.e., fevers), or if \geq grade 3 neutropenia recurs in a participant on sEphB4-HSA with growth factor support, treatment with sEphB4-HSA should be held for one week. If ANC recovers to \leq grade 2 within two weeks and additional toxicities resolve, if any, restart at a reduced dose by one level. If \geq grade 3 neutropenia or fevers persists at 14 days (2 weeks) despite growth factor support, sEphB4-HSA will be stopped. If grade 3 or 4 neutropenia subsequently recurs but ANC recovers to \leq grade 2 within two weeks, restart at a reduced dose by one level.

Table 5-D: Summary of dose modifications for neutropenia

OCCURRENCE	GRADE 3/4
1 st	
 Hold sEphB4-HSA until ANC \leq grade 2

OCCURRENCE	GRADE 3/4
	
 • Add growth factor (filgrastim or pegfilgrastim) if not already on growth factor. 
 ◦ If \leq grade 2 within 1 week, continue on study drug at current dose with growth factor. ◦ If not \leq grade 2 within 1 week, or additional infection-related toxicity seen (i.e., fever), hold sEphB4-HSA for another week and continue growth factor. ◦ If \leq grade 2 within 14 days (2 weeks) and infection-related toxicity, if any, resolves, restart sEphB4-HSA at reduced dose by one level. ◦ If not \leq grade 2 within 14 days (2 weeks), stop treatment.
2 nd	
 • Hold sEphB4-HSA until ANC \leq grade 2 • Add growth factor (filgrastim or pegfilgrastim) if not already on growth factor. 
 ◦ If \leq grade 2 within 14 days (2 weeks), restart sEphB4-HSA at reduced dose by one level. ◦ If not \leq grade 2 within 14 days (2 weeks), stop treatment.
3 rd – after first dose reduction	Stop treatment

Grade 3 or 4 Anemia

No dose reductions will be performed for grade 3-4 anemia. If the participant develops anemia, participant may be transfused or receive an available recombinant human erythropoietin preparation (epoetin alfa; darbepoetin alfa) at the discretion of the investigator.

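### Section 5.5 gives two different platelet recovery thresholds after a second grade 3/4 thrombocytopenia, and one stop sentence names a dose level that Table 5-A does not contain

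*Combined protocol and SAP*

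**What the plan says.** Section 5.5 opens with a general rule: "There will be no dose interruptions or reductions for any grade 1/2 hematological toxicity".

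For a **first** grade 3/4 thrombocytopenia, the text requires recovery to at most "grade 2 within 14 days (2 weeks). sEphB4-HSA treatment may then be resumed at dose that is reduced by one dose level". Row 1 of Table 5-C agrees.

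For a **second** event the text is stricter, and says so twice. The hold sentence reads "sEphB4-HSA must again be withheld until the toxicity level returns to < grade 2", and the restart sentence reads "If the toxicity again resolves to < grade 2 within two weeks, sEphB4-HSA may be recommenced", one level lower. Row 2 of Table 5-C instead holds until grade 2 or better within 14 days, "then resume at dose again reduced by one dose level".

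The same paragraph contains three stop sentences:

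- lowest level: "If sEphB4-HSA is at the lowest dose level, stop treatment"
- persistence: if at any time "the grade 3/4 toxicity persists for longer than two weeks, sEphB4-HSA will be stopped permanently"
- a named level: "If grade 3 or 4 thrombocytopenia recurs at dose level 1, treatment will be stopped permanently"

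Table 5-A (Section 5.1) lists level 0 (10 mg/kg), level -1 (7.5 mg/kg) and level -2 (5.0 mg/kg). Section 4.1 uses the name dose level 1 for the 15 mg/kg dose of versions before 4.0, now discontinued. Section 5.6 refers sites to Section 5.5, among others, for hold and stop parameters, and ends protocol therapy after an interruption of more than 28 days.

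**The concern.** These are working instructions on when to hold, restart and stop the drug in a multi-institutional trial. The text and its summary table give different actions for the same platelet recovery, and the document does not say which takes precedence. Two sites that each follow the protocol literally could dose participants in the same state differently, and an auditor could not say which had deviated.

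The dose level 1 sentence adds a second ambiguity. A site that takes it as level -1 with a lost minus sign would permanently stop a participant whom Table 5-C would treat at 5.0 mg/kg.

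**Working it through.** The plan states no figure to reproduce here. The check compares rules, with one short piece of arithmetic.

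**1. Recovery threshold, second grade 3/4 event**

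| State on day 14 | Section 5.5 text | Table 5-C, row 2 |
|---|---|---|
| Grade 0 or 1 | Restart one level lower | Restart one level lower |
| Exactly grade 2 | Keep holding | Restart one level lower |
| Grade 3 or 4, persisting beyond two weeks | Stop | Stop |

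Only the middle row differs. In that state the text's restart condition is not met, because grade 2 is not below grade 2. Its persistence stop is not met either, because the toxicity is no longer grade 3/4. What remains is the 28-day limit (Sections 4.5 and 5.6) or removal on the investigator's judgment (Section 4.5).

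**2. Doses affected (Table 5-A)**

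- Second event at level -1, the usual case after one reduction from 10 mg/kg: the table restarts at 5.0 mg/kg; the text holds at exactly grade 2.
- Second event at 10 mg/kg: the table restarts at 7.5 mg/kg; the text holds at exactly grade 2. This needs someone who started at 15 mg/kg and was already reduced. Section 10.1 gives n = 3 treated at 15 mg/kg; the documents do not say whether any was reduced or is still on treatment.
- Second event at level -2: text and table both stop.

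**3. Length of the period without a thrombocytopenia-specific rule**

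Inputs: the two-week recovery window (Section 5.5), the 28-day limit (Section 5.6), a 14-day dosing interval, and laboratory tests allowed up to 7 days before the due dose (Section 8.2.2). Sections 5.5 and 5.6 do not say when their clocks start. I assume that the 28-day clock starts at the withheld dose and the two-week clock starts at the blood count, taken L days earlier (L = 0 to 7).

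Gap = 28 − (14 − L)

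- L = 0: 28 − 14 = 14 days; 14/14 = 1.0 dosing interval
- L = 7: 28 − 7 = 21 days; 21/14 = 1.5 dosing intervals

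**4. Possible readings of dose level 1**

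- As 15 mg/kg (Section 4.1): that dose is discontinued, so the sentence has no current use.
- As the lowest level: it repeats the lowest-level stop already in the paragraph.
- As level -1: it stops treatment where the preceding restart sentence and Table 5-C row 2 both allow a further reduction to level -2.

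No reading gives the sentence a useful role, and the third contradicts the rest of the section.

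**The case against.** The strongest counter-argument is that the first part rests on a single symbol in machine-read text, where an underlined less-than sign can lose its bar. The document has other strict and non-strict mismatches: the raised-lesion threshold in Section 9.1.4 (at most 8, then below 8), the Karnofsky cut-off in Appendix VII (above 70 in the table, at least 70 in its note), and the biopsy lesion size (at least 5 mm in Section 3.1.8, above 5 mm in Section 8.1.9). This stands in part: only the PDF can exclude it. Against it, the strict form appears twice in a paragraph that also prints the non-strict form correctly, and a lost bar would not explain dose level 1.

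A second argument is that the section resolves the conflict itself. The opening rule, the first-event rule, Table 5-C and the neutropenia recovery criteria all accept grade 2. That is good evidence of what was intended, and it is why the fix below follows the table. It does not tell a site which wording to obey, and Table 5-C is titled a summary, so a site could equally treat the text as controlling.

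Third, the text can be read as implying no restart if recovery below grade 2 takes longer than two weeks, with the 28-day limit as a backstop, so the literal reading errs towards caution. That is fair. The missing piece is an explicit rule, and the worst outcome under this wording is an unneeded hold or discontinuation.

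Finally, the event is rare: two grade 3/4 platelet events in one of at most 20 participants, the second at exactly grade 2 on day 14, and Table 6-C lists decreased platelets among risks not reported in prior trials. This supports a minor rating but does not remove the contradiction.

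**Conclusion.** Both inconsistencies are present as the document reads, and the point is **minor**. The different action is confined to a second grade 3/4 thrombocytopenia that stands at exactly grade 2 on day 14 at level -1, or possibly at 10 mg/kg in a former 15 mg/kg starter. The table then gives a one-level-lower restart and the text a continued hold. The period without a specific rule, 14 to 21 days, depends on the assumed clock starts. The documents give no event rate, so I do not estimate how many participants would be affected.

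The primary decision rule in Section 10.2 (at least 9 responders and no more than 3 participants with unacceptable toxicity), the sample size of 20 and the unacceptable-toxicity definition in Section 10.1 are unchanged.

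**What to change.** In the thrombocytopenia paragraph of Section 5.5:

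1. Change both second-event thresholds from below grade 2 to grade 2 or better, to match Table 5-C and the first-event rule.
2. Delete the sentence on recurrence at dose level 1, since the lowest-level stop is already stated, or change the level to -2.

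If the sponsor does intend the stricter rule (recovery to grade 1, or a permanent stop at level -1), leave the text's threshold, write level -1 explicitly where that is meant, and amend Table 5-C and any conflicting restart sentence to match.

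The change is two symbols and one sentence, with no new data, visits or participants. Section 12.2 requires CTEP and IRB approval for any amendment, so it is best carried in the next one rather than issued alone.

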5.6 Dose Interruptions

Participants who have a delay in administration of a dose of the study drug of ≤ 48 hours should take the planned dose as soon as possible after the intended time of administration and continue on the same 28-day cycle (i.e., Day 15 of the same cycle will not change if Day 1 is delayed, or the next cycle start date Day 1 will not be delayed). Relevant evaluations due prior to the next sEphB4-HSA dose may be delayed accordingly.

For participants who have a delay in administration of study drug of >48 hours but ≤ 28 days (please refer back to [Sections 5.2](#), [5.3](#), and [5.5](#) for hold and stop parameters for non-hematologic and hematologic toxicities), the study drug administration may continue with the following instructions: If the Day 1 dose of any new cycle is delayed ≥ 48 hours, that cycle start date and subsequent treatment days and cycles will be reset. If the Day 15 dose of is delayed ≥ 48 hours, the following Day 1 dose of the next cycle will not be given until 14 days later. All relevant evaluations will be delayed accordingly.

Any dose interruption of more than 28 days requires discontinuation of protocol therapy.

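### Section 5.5 text and Table 5-D give different neutropenia instructions: restart versus stop at a recovered third episode, and optional versus required hold at the first

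*Combined protocol and SAP*

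**What the plan says.** Section 5.5 gives the rules for grade 3 or 4 neutropenia (ANC below 1 x 10⁹/L) twice, in prose and in Table 5-D.

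**First episode.** The prose says "treatment with sEphB4-HSA may be interrupted and growth factor (filgrastim or pegfilgrastim) should be started at standard doses". If ANC is back to grade 2 or lower within a week with no additional toxicity, "treatment with sEphB4-HSA may continue without dose modification with continued growth factor support". Row 1 of Table 5-D opens with "Hold sEphB4-HSA until ANC" is grade 2 or lower, then gives the same dosing outcome for recovery within a week.

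**Slow recovery, additional toxicity such as fever, or recurrence on growth factor.** The prose becomes firm: if "neutropenia recurs in a participant on sEphB4-HSA with growth factor support, treatment with sEphB4-HSA should be held for one week". Recovery within two weeks leads to a restart one level lower; no recovery by 14 days stops treatment. Row 2 of the table agrees for a second episode.

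**Later recurrence.** The last prose sentence reads "If grade 3 or 4 neutropenia subsequently recurs but ANC recovers to" grade 2 or lower within two weeks, followed by a restart one level lower. Row 3 of the table, for a third occurrence "after first dose reduction", stops treatment and makes no exception for recovery.

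The dose levels in Table 5-A are 10, 7.5 and 5.0 mg/kg. Section 5.6 sends sites back to Section 5.5 "for hold and stop parameters for non-hematologic and hematologic toxicities". Section 4.5 makes the Section 5.0 criteria grounds for removal from treatment. No provision says whether prose or table governs where they differ.

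**The concern.** Sites act on these rules directly, and the trial is multi-institutional. If prose and table give different instructions for the same participant, one site can discontinue permanently while another restarts at a lower dose, both in good faith. At the first episode, a site following the prose could give a dose while ANC is still below 1 x 10⁹/L, which the table does not allow. What is at stake is participant safety and consistent treatment across sites. The decision rule on 20 participants does not depend on it.

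**Working it through.** No statistical figure in the plan is involved. The check takes the prose and the table through successive episodes, starting at the current dose of 10 mg/kg and using the Table 5-A levels.

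**Path A: first episode recovers within one week**

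| Episode | Section 5.5 prose | Table 5-D | Agree? |
|---|---|---|---|
| 1, dose after recovery | 10 mg/kg | 10 mg/kg | Yes |
| 2, recovers within 2 weeks | 7.5 mg/kg | 7.5 mg/kg | Yes |
| 3, recovers within 2 weeks | restart one level lower, 5.0 mg/kg | stop | **No** |

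At episode 3 exactly one reduction has been made, so the participant matches the row 3 label, and a lower level is still available for the prose to use.

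**Path B: first episode recovers only in the second week, or with fever**

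| Episode | Section 5.5 prose | Table 5-D | Agree? |
|---|---|---|---|
| 1, dose after recovery | 7.5 mg/kg | 7.5 mg/kg | Yes |
| 2, recovers within 2 weeks | 5.0 mg/kg | 5.0 mg/kg | Yes |
| 3 | no lower level exists | stop | No practical conflict |

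The restart-or-stop conflict is therefore confined to Path A. On both paths, prose and table agree on stopping when there is no recovery by 14 days.

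**Action on the drug at the first episode (both paths).** The prose verb is permissive; the table's is directive. The thrombocytopenia rule in the same section is mandatory ("sEphB4-HSA must be withheld until the toxicity has resolved to" grade 2 or lower), so the softer verb for neutropenia reads as a real permission.

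Timing makes this matter. Sections 8.2.1.8 and 8.2.2 place the CBC 0 to 7 days before each Day 1 and Day 15 dose, and doses are 14 days apart. For a CBC drawn d days before a dose (d = 0 to 7), the following doses fall at d, d + 14, and so on. Exactly one of these, the dose at day d, lies within the first 7 days. So when a scheduled CBC detects a first episode, one scheduled dose comes due before the prose hold for non-recovery at one week takes effect.

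**Illustration of the exposure at issue on Path A.** Assume treatment would otherwise run the full 12 cycles: 12 x 2 = 24 doses. If the third episode resolves before Day 1 of cycle c, the remaining doses are (12 − c + 1) x 2:

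- c = 4: 9 x 2 = 18
- c = 7: 6 x 2 = 12
- c = 10: 3 x 2 = 6

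The table gives 0 in each case. These figures are an illustration, not a bound or an expected value.

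**The case against.** **Section 4.5 may already settle the third episode.** It requires removal when any Section 5.0 criterion applies, and row 3 of Table 5-D is such a criterion. This has force and is a good reason to take the table's rule as the default. It does not remove the prose sentence that tells the site to restart.

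**The closing prose sentence may cover only a second episode.** The preceding prose deals with recurrence in someone already on growth factor, whereas row 2 also provides for a participant who is not. The last sentence could supply the rule for that case, with the same outcome as row 2. This reading is possible. But nothing limits the sentence to a second occurrence, and the prose has no third-occurrence stop. The neighbouring thrombocytopenia rule allows two reductions, so a reader could expect the same here.

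**The first-episode difference may be loose drafting.** Permission to continue once ANC recovers arguably implies waiting for recovery, fever triggers the firm hold sooner, and a site that holds complies with both versions. For a CBC drawn 7 days ahead, the one-week recovery check falls on the dosing day. The timing argument shows only that a dose comes due, not that it would be given. All of that stands. What remains is that a site dosing at an unrecovered ANC could point to the prose while breaching the table.

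**The branch is rare.** The first conflict needs three separate grade 3/4 episodes in one participant, each with the specified recovery, and the plan gives no neutropenia rate. This is accepted and limits the importance of the point.

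**Conclusion.** Both discrepancies are in the current text.

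- **Third episode:** after a fast-recovering first episode and one reduction, a recovered third episode leads to 5.0 mg/kg under the ordinary reading of the prose and to permanent discontinuation under the table.
- **First episode:** the prose permits a dose that the table says to hold. One scheduled dose is exposed for each first episode found on a scheduled CBC.

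The impact is low. Few of the 20 participants are likely to be affected: neutropenia is not listed in Tables 6-A to 6-C, and the nearest term, a decreased white cell count, is in Table 6-C among risks not reported in prior trials. That term is an imperfect proxy, because Section 5.5 bases dosing on ANC and not on the white cell count. The primary endpoint definition, the sample size and the power do not change. The conclusion assumes a start at 10 mg/kg and the ordinary reading of the closing prose sentence. It should be corrected because it concerns dosing safety and wording alone resolves it.

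**What to change.** **First episode.** Change the prose to: *sEphB4-HSA must be held until ANC is grade 2 or lower.*

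**Recurrence, default (the table's rule, in line with Section 4.5).** Limit the closing prose sentence to the second occurrence, add *at a third occurrence, stop treatment*, and relabel row 3 of Table 5-D simply as *3rd occurrence*. This gives one answer on both recovery paths.

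**Recurrence, if the sponsor intends two reductions.** Relabelling row 3 is not enough. Table 5-D then needs a rule for a recovered third episode after only one reduction: hold; if grade 2 or lower within 14 days, restart one level lower; if already at the lowest level, stop. The same lowest-level stop must be added to the prose.

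**Cost.** The default is amendment wording only: two prose sentences revised, one stop clause added and one row label changed. The alternative needs the first-episode change, one new or rewritten table row and one prose clause. Neither changes the sample size, visits or data collection.
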